5.2 Phases of the Project

The following activities will be performed during the proposed project, by phase:

Design Phase (months 1-9)

1. Organize Northwestern-Walgreens-ACCESS team; establish project milestones, roles.
2. Convene all stakeholders (primary care providers, Walgreens pharmacists and leadership) to gather feedback on the initial draft standard operating protocol (SOP) for the implementation of TEAM in ACCESS clinics, leveraging Walgreens pharmacists will be developed. This is an iterative process with all TEAM users.
3. Amend existing Walgreens-ACCESS agreements to include new Epic read/write access, given the parameters established by the mutually-agreed upon SOP. This includes the specification of set security points within the ACCESS EHR (Epic) that both allows and controls pharmacist permissions. Our Northwestern team has already worked with ACCESS and Walgreens to detail the TEAM protocol (see section 4.0 study intervention).
4. Devise an implementation evaluation battery capturing process outcomes and also a range of patient-reported medication safety-related outcomes.

Implementation phase (months 10-30)

5. 'Beta test' the TEAM strategy in the clinical environment to confirm the functionality of all bi-directional information sharing components.
6. Trouble shoot any technical/procedural concerns, modifying the SOP accordingly.
7. Orient participating ACCESS clinical sites and Walgreens staff on the final SOP in preparation for the live implementation to be conducted in the second project phase.
8. Implement the finalized TEAM intervention protocol defined in the Design Phase at ACCESS clinic sites. The strategy includes Walgreens pharmacist outreach with identified

STU#: STU00209066

ACCESS patients to: a) perform medication reviews, b) generate automatic and tailored EHR-based alerts; c) provide clinical decision support.

9. Enroll 120 patients into the pilot study.
10. Randomize patients (1:1) to either: 1) the TEAM intervention or 2) enhanced usual care.
11. Conduct baseline (by phone) and 2 month follow-up interview (by phone) with enrolled patients. Interviews will include validated measures and will be completed using RedCAP software for data quality and safety. Data will also be abstracted from patient EHR records at 12 months post-enrollment.

Evaluation Phase (months 31-36)

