Clinical Markers. We will abstract relevant clinical markers (e.g. HBA1c for patients with diabetes, LDL cholesterol for patients with hypercholesterolemia, blood pressure for patients with hypertension). Multiple blood pressure measures will be averaged for analyses in accordance with current protocols.

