9.1 Inclusion Criteria

Patients meeting inclusion criteria 1-5 below will be identified through ACCESS EHR data pulls on a quarterly basis. For those who qualify for the study based on these pulls, Northwestern RCs will contact these patients by phone to complete an initial phone screener during which time they will confirm criteria 1, 2, 5, and 6 as well as ensure that they do not meet any exclusion criteria.

- 1) Patient is age 50 and older
- 2) Patient is English or Spanish speaking
- 3) Patient has established care at one of the involved ACCESS health centers (defined as 1 visit within 18 months)
- 4) Patient is an existing Walgreens customer (had 1 or more medications filled at collocated Walgreens pharmacy within past 12 months)
- 5) Patient is currently prescribed 5 or more Rx medications (excluding antibiotics); that includes at least one medication from any of the following six therapeutic classes of medications: hyperlipidemia, hypertension, diabetes, multiple sclerosis, hepatitis C, and HIV
- 6) Patient is primarily responsible for administering own medication

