17.0 Data Management and Confidentiality

17.1 Analysis Plan

All analyses will be performed in SAS v9.4 (SAS Institute, Cary, NC). [name] will perform analyses under the direct supervision of [name] and Drs. [name] and [name].

Aim 1. Evaluate the fidelity and efficacy of the TEAM intervention to promote healthcare provider counseling, medication reconciliation, and safe regimen use among adults taking complex Rx regimens.

Quantitative analyses will be performed using SAS v9.4 (SAS Institute, Cary, NC). To ensure adequate balance across treatment arms, baseline outcomes and potential confounders including socio-demographic characteristics, comorbidities, regimen complexity, health literacy

STU#: STU00209066

level will be compared using ANOVA models and χ^2 tests, as appropriate. Variables found to have significant differences ($p < .05$) across treatment groups will be entered as covariates in the generalized linear mixed models (GLMMs) used for formal analyses as described below. Treatment arm will serve as the primary independent variable. Analyses will be performed using PROC GLMMIX in SAS (v.9.4). A binary variable will be included in the model to denote the intervention group vs. usual care. As we will use stratified randomization by site, we will include in the GLMM an indicator variable for site and any potential confounding covariates noted in the descriptive studies. For outcomes assessed for each medication, 2-level GLMM will be used with medications nested in participants. Additionally, as there may be some effect of provider on adherence, we will explore the effect of any PCP by including provider as a random-effect. Using similar models as described above, we will assess the impact of TEAM on clinical markers (HbA1c, blood pressure, cholesterol) among patients with diabetes and hypertension.

Aim 2. Explore patient, healthcare provider (pharmacist, prescriber), community pharmacy and/or primary care practice barriers to implementation.

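### Section 17.1 analyses HbA1c, blood pressure and cholesterol in patients with diabetes and hypertension, which does not match the marker-by-marker pairing in 5.5 and leaves out patients whose only relevant condition is hyperlipidemia.

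*Combined protocol and SAP*

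**What the plan says.** Section 5.5 (Clinical Markers) gives each marker its own patients. It opens "We will abstract relevant clinical markers (e.g. HBA1c for patients with diabetes" and continues "LDL cholesterol for patients with hypercholesterolemia, blood pressure for patients with hypertension". The list is introduced as examples, so it does not expressly rule out abstracting a marker in other patients.

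Section 17.1 (Aim 1) reuses the Aim 1 models for these markers: "we will assess the impact of TEAM on clinical markers (HbA1c, blood pressure, cholesterol) among patients with diabetes and hypertension". It names three markers and two conditions. Hypercholesterolemia is the one left out, and the lipid marker is called cholesterol rather than LDL.

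Section 9.1, criterion 5, requires five or more prescription drugs including "at least one medication from any of the following six therapeutic classes of medications: hyperlipidemia, hypertension, diabetes, multiple sclerosis, hepatitis C, and HIV". A lipid drug is therefore sufficient on its own to meet the class requirement.

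On timing, section 5.2 says "Data will also be abstracted from patient EHR records at 12 months post-enrollment". Section 17.1 enters baseline variables as covariates only if they differ between arms at p<.05.

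**The concern.** The analysis population decides who contributes to each estimate, and here two sections define it differently. Improving lipid-drug adherence is part of the intervention: section 4.1 lists hyperlipidemia among the classes in the adherence report sent to the pharmacist. Patients whose only relevant condition is a lipid disorder are among those in whom an LDL effect would be expected, yet 17.1 gives them no place in the lipid model.

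The phrase naming the two conditions can also mean either or both. The two readings give different datasets for all three markers, and nothing elsewhere in the document settles which is meant. With 60 patients per arm before any restriction by condition, the choice could change the result, and it should be written down before analysis.

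**Working it through.** The documents state no power, effect size, standard deviation or prevalence for these analyses, so there is no plan figure to reproduce. The check is a comparison of texts, followed by two illustrations on assumed inputs.

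**Step 1. Compare the definitions.** The pairing comes from 5.5, the analysis set from 17.1, and the enrolment route from 9.1.

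| Marker | Patients under 5.5 | 17.1 read as either condition | 17.1 read as both conditions |
|---|---|---|---|
| HbA1c | Diabetes | Adds hypertension without diabetes, where HbA1c is abstracted for them | Loses diabetes without hypertension |
| Blood pressure | Hypertension | Adds diabetes without hypertension, where abstracted | Loses hypertension without diabetes |
| LDL | Hypercholesterolemia | Loses those with neither condition; adds patients without a lipid disorder only if LDL is abstracted for them | Loses those lacking at least one of the two; same proviso on additions |

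Neither reading reproduces the 5.5 set for any marker. Under both readings, patients with hypercholesterolemia alone are lost from the lipid model.

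**Step 2. Share of hypercholesterolemia patients left out (illustration).** Assume, among them, hypertension prevalence h = 0.70 to 0.90 and diabetes prevalence d = 0.40 to 0.60, independent of each other. None of this is in the documents.

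- Either condition: share left out = (1-h)(1-d). This runs from 0.10 × 0.40 = 0.04 to 0.30 × 0.60 = 0.18.
- Both conditions: share left out = 1 - hd. This runs from 1 - 0.90 × 0.60 = 0.46 to 1 - 0.70 × 0.40 = 0.72.

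The loss is about 4-18% under one reading and 46-72% under the other.

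**Step 3. Dilution, only if LDL is abstracted beyond hypercholesterolemia (illustration).** Let n be the analysed number, f the fraction with no lipid disorder, and δ the effect in lipid patients. Assume no effect in the rest and equal standard deviations.

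- Average effect in the mixed set: δ(1-f), which is 80% of δ at f = 0.2 and 60% at f = 0.4.
- Information in the mixed set is proportional to n × [δ(1-f)]² = nδ²(1-f)².
- Restricting the same sample to lipid patients leaves n(1-f) patients with effect δ, so information is proportional to nδ²(1-f).
- Efficiency ratio, restricted to mixed: (1-f)/(1-f)² = 1/(1-f).

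| f (assumed) | 1/(1-f) |
|---|---|
| 0.2 | 1.25 |
| 0.3 | 1.43 |
| 0.4 | 1.67 |

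These ratios do not count any hyperlipidemia-only patients regained by the fix, whose number is unknown.

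**The case against.** The best defence is that 17.1 is loose shorthand. Read with 5.5 and with the separate drug classes in 9.1, it may simply mean each marker in the patients to whom it is relevant, with the third condition forgotten. No text shows an intention to require both diabetes and hypertension. That is plausible, but it is an inference: the sentence that governs the analysis says something else, and no other section corrects it.

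A reader might infer that the lipid result would come from the wrong patients altogether. The documents do not support that. If LDL is abstracted only in hypercholesterolemia, applying both sections gives the overlap, a subset of the intended patients. There is then no dilution, only loss. Dilution needs wider abstraction, which the 'e.g.' in 5.5 allows but does not state.

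A reader might also put the cost of dilution at 1/(1-f)², which is 1.56 to 2.78 for f between 0.2 and 0.4. That compares the mixed set with an equally large sample made up entirely of lipid patients, which restricting the analysis would not deliver. Because restriction also reduces the number analysed, the relevant ratio is 1/(1-f).

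Three further points stand in part.

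- Section 5.4 blinds the statistical staff and investigators to arm. This lowers the risk of choosing a population by its result, but does not replace writing the choice down.
- A hypercholesterolemia set may still contain untreated patients, so assuming the effect is confined to patients with the disorder is a simplification.
- Adjustment for the baseline marker is a separate improvement. It does not follow from the population mismatch.

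**Conclusion.** The point holds as an inconsistency between 17.1 and 5.5. Following 17.1 literally leaves patients with hypercholesterolemia alone out of the lipid analysis. Under the either reading it can also bring patients without the matching condition into the HbA1c and blood pressure models; under the both reading it shrinks those sets.

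The size cannot be stated from the documents, because they give no condition mix. The 1.25 to 1.67 range rests on an assumed f of 20-40%, no effect outside lipid patients, equal variances, and LDL being abstracted beyond hypercholesterolemia. The exclusion shares in the working rest on assumed, independent prevalences.

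Severity is modest. Aim 1 concerns counseling, reconciliation and safe regimen use, and does not name the clinical markers. The trial is a 120-patient pilot with no designated primary efficacy outcome and no stated power, so no planned power is lost. The correction is worth making because it is cheap and removes an open choice.

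**What to change.** Replace the clinical-marker sentence in 17.1 with one that states:

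- HbA1c is analysed among patients with diabetes at baseline, blood pressure among patients with hypertension at baseline, and LDL cholesterol among patients with hypercholesterolemia at baseline.
- Each condition is taken from the baseline EHR by the same rule in both arms.
- Each model includes the patient's last pre-randomisation value of its marker as a covariate, whatever the p<.05 balance test shows.

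Use LDL cholesterol in both 5.5 and 17.1. If another population is intended, 17.1 should say which.

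The cost is a short text change and no new patient contact. The EHR pull must include pre-randomisation marker values; sections 5.2 and 8.0 schedule the abstraction at 12 months without stating a look-back window. Patients with no earlier value need a simple rule fixed in advance, for example a missing-value indicator with a constant filled in without regard to arm.

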18.0 Provisions to Monitor the Data to Ensure the Safety of Participants

18.1 Data Safety and Monitoring Board (DSMB)

This study involves no greater than minimal risk. Due to this, we will not be convening a DSMB for this study.

19.0 Provisions to Protect the Privacy Interests of Participants

19.1 Information about study subjects will be kept confidential and managed according to the requirements of the Health Insurance Portability and Accountability Act of 1996 (HIPAA). In order to preserve participants’ confidentiality rights, research subjects will be assigned code numbers that will be used to identify all the information collected. Using these codes, none of the collection forms will contain the names of the participants. All electronic data will be stored in on a password-protected computer. A Microsoft Access master study tracking database will contain information linking participants to their study id numbers. This database will be encrypted and kept on a secure server and only accessible by study personnel.

19.2 Survey data will be stored in a REDCap. Individual study identification numbers will be assigned to each participant and only this number will appear on the survey. Subjects will be told that unless required by law, only the study investigators, members of the project staff, the funding agency and representatives of Institutional Review Boards will have the authority to review any study records. In such cases, these parties too will be required to maintain confidentiality. The final data set will be stripped of identifiers. Data will be shared via presentations at national and international meetings and in peer reviewed publications. Furthermore, all results will be shared with the funding institute.

STU#: STU00209066

19.3 Participation in the study poses minimal risk of psychological, social and economic harm. Informing subjects in advance that they may decline to answer any questions asked during the interview will mitigate any risks associated with expressing their opinions (e.g., feeling uncomfortable).

19.4 All enrolled participants will provide e-consent, include HIPAA authorization for the collection of all data, including review of the patient's medical record. For those who are unable to provide e-consent due to inability to access the required technology, they will undergo verbal consent with an alteration of HIPAA Authorization, as described below in sections 22.0 and 24.0.

19.5 Only authorized personnel listed on each institutions IRB and approved by the PI will have access to the data.

20.0 Compensation for Research-Related Injury – N/A

21.0 Economic Burden to Participants – N/A

22.0 Consent Process

22.1 Process to Document Consent in Writing

Due to COVID-19 in-person interview restrictions, we will complete an online consent with HIPAA authorization and complete the baseline by phone after consent is obtained. The RC will send patients a link to REDcap either by email or text to be able to read through the consent with the RC following the protocol below. If the patient agrees to participate, they will be asked to sign and date the online consent.

If a patient is unable to complete an online consent due to inability to use or access technology for online consent, we request a waiver of documentation of informed consent and an alteration to obtain verbal HIPAA Authorization. Due to restrictions during the COVID-19 pandemic, we are no longer planning to conduct any in-person interviews to protect patients' safety and to follow Northwestern guidelines. Research cannot practicably be conducted without the waiver or alteration. For patients that are unable to complete online consent, research cannot practicably be conducted without the waiver or alteration. After verbal consent and HIPAA Authorization is obtained, the consent date and the name of the research coordinator that obtained the consent will be recorded in Redcap by the RC prior to starting the baseline interview.

Informed online and verbal consent will be viewed as a process, i.e. at several times during review of the IRB approved consent document, the subject will be asked to explain in his/her own words what his/her understanding of the consent. This will enable the research personnel to enter into a dialogue with the subject and ensure that the subject understands that he/she is free to withdraw at any time without penalty. Information will be provided to the subjects in terms that they can fully understand. There will be no exertion of any overt or covert coercion. They will be encouraged to ask questions prior to giving consent.

The participant will be informed that they are free to withdraw at any time without penalty and all information will be provided to the subjects in terms that they can fully understand. Once the RC

STU#: STU00209066

is satisfied that the participant understands the consent process and the nature of their participation in the research study, the RC will ask the participant if they would like to participate in the study.

For online consents, patients will be informed they can print their screen to keep a copy of the consent. For patients that complete a verbal consent, they will be emailed or mailed a blank copy of the consent document for their records.

23.0 Non-English Speaking Participants

All study materials are available in both English and in Spanish and our RCs are bilingual. We have included Research Support Services as part of the grant to provide Spanish translations for materials that have yet to be created. Patients who do not speak either Spanish or English will be ineligible to participate. Patients will be asked their language of choice as they are consented. Research coordinators will be able to conduct all interviews and schedule phone calls in either language. Pharmacists delivering the intervention will do so in the patient's preferred language.

24.0 Protected Health Information (PHI and HIPAA)

24.1 Information about study subjects will be kept confidential and managed according to the requirements of the Health Insurance Portability and Accountability Act of 1996 (HIPAA). In order to preserve participants' confidentiality rights, research subjects will be assigned code numbers that will be used to identify all the information collected. Using these codes, none of the collection forms will contain the names of the participants. All electronic data will be stored in on a password-protected computer. A Microsoft Access master study tracking database will contain information linking participants to their study id numbers. This database will be encrypted and kept on a secure server and only accessible by study personnel.

Survey data will be stored in a REDCap. Individual study identification numbers will be assigned to each participant and only this number will appear on the survey. Subjects will be told that unless required by law, only the study investigators, members of the project staff, the funding agency and representatives of Institutional Review Boards will have the authority to review any study records. In such cases, these parties too will be required to maintain confidentiality. The final data set will be stripped of identifiers. Data will be shared via presentations at national and international meetings and in peer reviewed publications. Furthermore, all results will be shared with the funding institute.

24.2 All enrolled participants will provide either e-consent or verbal consent, which will include HIPAA authorization for the collection of all data, including review of the patient's medical record. For patients who are unable to provide e-consent and signed HIPAA Authorization, we are requesting an alteration of HIPAA Authorization in order to obtain HIPAA Authorization verbally. These patients would otherwise be unable to participate in this research study and therefore this research could not practicably be conducted without this alteration in place. Only authorized personnel listed on each institutions IRB and approved by the PI will have access to the data.

STU#: STU00209066

Due to restrictions during the COVID-19 pandemic, we are no longer planning to conduct any in-person interviews to protect patients' safety and to follow Northwestern guidelines. If a patient is unable to complete an online consent due to inability to use or access technology for online consent, we request a waiver of documentation of informed consent and an alteration to obtain verbal HIPAA Authorization. For these patients that are unable to complete online consent, research cannot practicably be conducted without this waiver or alteration. After verbal consent and HIPAA Authorization are obtained, the consent date and the name of the research coordinator that obtained the consent will be recorded in Redcap by the RC prior to starting the baseline interview.

As this research could not practicably be conducted without the waiver or alteration of HIPAA, it could also not practicably be conducted without access to and use of PHI. The main intervention component of this study involves a pharmacist reviewing the patient's medications with them and making notes (with EPIC security points in place) in their EHR for the patient's provider to see. It would not be feasible to conduct the study and implementation of the intervention without the access and use of PHI.

Identifiers and other related information for coordinating research activities (recruitment outcome, research interview call log and interview visit schedule, etc.) will be password protected and kept on the secure FSM network drive. Only the PI, project manager, and RAs will have access to this database. Identifiers included in the database include: name, MRN, address, phone number, DOB. Upon completion of all study-related data collection the Access database will be deleted. Study generated data will be stored within REDCap and OneDrive and will be downloaded (void of all identifiers) into the project's Analytic folder on the FSM server. Upon completion of the study, a final dataset, void of all identifiers will be created, and stored indefinitely for secondary analyses.

PHI will not be used or disclosed to a third party except as required by law, for authorized oversight of the research study, or for other research uses and disclosures permitted by the Privacy Rule.

